8.2 Blinding

All patients will be blinded to the treatment groups as they will receive the one-time treatment while under general anesthesia in the operating room.

All study staff will be blinded to the treatment groups, except those staff involved in assigning treatment groups. Access to the randomization code will be strictly controlled. The study blind will be broken on completion of the clinical study and after the study database has been locked.

Investigators will be blinded to the medical treatment groups - Standard Bupivacaine and Liposomal Bupivacaine. As Standard Bupivacaine is clear and Liposomal Bupivacaine is milky white, obscuring over-wraps will be placed over syringe. See Section 8.3-8.3.2 for more information.

During the study, the blind may be broken only in emergencies when knowledge of the patient's treatment group is necessary for further patient management. If this occurs, the investigator will contact the study staff involved in assigning treatment groups, and the blind will be broken. When possible, the investigator should discuss the emergency with the Medical Monitor prior to unblinding.

8.3 Formulation of Test and Control Products

Study Treatment

Liposomal Bupivacaine - Exparel[®]

- Manufacturer: Pacira Pharmaceuticals Inc - Parsippany, NJ
- Formulation: Suspension, Injection
- Preparation: See Section 8.3.1

Active Comparator

Standard Bupivacaine - Marcaine[®]

- Manufacturer: Hospira Inc - Lake Forest, IL
- Formulation: Suspension, Injection
- Preparation: See Section 8.3.2

The study treatment and active comparator will be prepared by the Investigational Pharmacy under aseptic conditions and used within 24 hours.

8.3.1 Formulation of Test Product (See Table 1 in Section 8.3.2)

Liposomal Bupivacaine

- Drug Preparation: 266mg (20cc) Liposomal Bupivacaine admixed with 0.25% (2.5mg/cc) Standard Bupivacaine* and varied 0.9% normal saline volume for total volume of 60cc.
 - 266mg (20cc) Liposomal Bupivacaine is the FDA-approved dose for wound infiltration.
 - Standard Bupivacaine is added to bridge the time to efficacy of Liposomal Bupivacaine, which occurs in 6-8 hours. This is standard clinical practice.
 - Normal saline is used to dilute the drug in order to have sufficient volume to perform the intervention.
 - As Standard Bupivacaine is clear and Liposomal Bupivacaine is milky white, obscuring over-wraps will be placed over syringe.

*If subject weight ≥ 35 kg, 30cc Standard Bupivacaine will be used. If subject weight < 35 kg, maximum dose of 2mg/kg Standard Bupivacaine will be used.

8.3.2 Formulation of Control Product

Standard Bupivacaine

- Drug Preparation: 0.25% (2.5mg/cc) Standard Bupivacaine* admixed with varied 0.9% normal saline volume for total volume of 60cc.
 - Normal saline is used to dilute the drug in order to have sufficient volume to perform the intervention.
 - As Standard Bupivacaine is clear and Liposomal Bupivacaine is milky white, obscuring over-wraps will be placed over syringe.

*If subject weight ≥ 35 kg, 30cc Standard Bupivacaine will be used. If subject weight < 35 kg, maximum dose of 2mg/kg Standard Bupivacaine will be used.

Table 1: Drug Preparation

| | Liposomal Bupivacaine | 0.25% Standard Bupivacaine |
|-------------------------------------|------------------------------|-----------------------------------|
| Active Ingredient: cc (mg) | 20 (266) | 30 (75)* |
| 0.9 % Normal Saline: cc | 10 | 30 |
| 0.25% Standard Bupivacaine: cc (mg) | 30 (75)* | n/a |

* If subject weight < 35 kg, maximum dose of 2mg/kg will be used.

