2.1 Risk / Benefit Assessment

The risks associated with Liposomal Bupivacaine and Standard Bupivacaine are similar. The most common adverse events include nausea, emesis, and/or constipation and are

expected to occur in >10% of subjects. Less common adverse events include dizziness, altered mental status, and hypersensitivity reactions with urticaria and/or pruritis. Very rare, but serious adverse events include neurologic toxicity with seizures and apnea, cardiac toxicity with atrioventricular nodal conduction abnormalities and cardiac arrest, and hypersensitivity reaction with anaphylaxis. Serious adverse events can be preventable with appropriate education, dosing, and administration. Most serious adverse events are found to be dose-related due to improper intravascular injection, inappropriate dosing, or slow metabolic degradation in patients with hepatic dysfunction [6]. For more information regarding adverse events, see prescribing information [2].

To minimize risk and limit the occurrence of serious adverse events, subjects will not be eligible for the study if they have evidence of hepatic dysfunction. In the operating room, dosing of Standard Bupivacaine will be based upon subject weight (See Section 8.3.2). The medication will be administered with proper technique by drawing back before injection to ensure the tip of the needle is not located within the lumen of a blood vessel. On the hospital ward, continuous cardiac telemetry will be used on all subjects and nursing will assess the mental status of each subject per shift.

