6.2 Inclusion Criteria

1. Robot or video-assisted lung resection for all indications
Robotic or video-assisted techniques both use three to four incisions that are <15mm and there are no expected differences between the techniques. The indication for surgery is not expected to influence the primary outcome.
2. Surgeons: [name] MD, [name] MD, or [name] MD
3. Written informed consent obtained from subject or subject's legal representative and ability for subject to comply with the requirements of the study.

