8.4.1 Dosage/Dosage Regimen

See Sections 8.3.1 and 8.3.2 for Drug Preparation.

Liposomal Bupivacaine

- 5cc of drug preparation will be injected into each intercostal space 3-10 and subcutaneously into each wound.

Standard Bupivacaine

- 5cc of drug preparation will be injected into each intercostal space 3-10 and subcutaneously into each wound.

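### The 35 kg dosing cut-off does not match the 2 mg/kg maximum: the fixed 75 mg equals 2 mg/kg only at 37.5 kg, and at 35 kg the prepared dose is 2.14 mg/kg

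*Combined protocol and SAP*

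**What the plan says.** Section 8.3.2 describes the control preparation as "0.25% (2.5mg/cc) Standard Bupivacaine* admixed with varied 0.9% normal saline volume for total volume of 60cc". Its footnote sets the amount by weight. At 35 kg or above, "30cc Standard Bupivacaine will be used" (the same words stand in Section 8.3.1 for the bupivacaine admixed in the test arm). Below 35 kg, a "maximum dose of 2mg/kg Standard Bupivacaine will be used". Table 1 prints the fixed amount as 30 cc (75 mg) in both arms, and its footnote repeats that below 35 kg a "maximum dose of 2mg/kg will be used".

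Section 8.4.1 governs how much is injected: "5cc of drug preparation will be injected into each intercostal space 3-10 and subcutaneously into each wound". Section 6.2 gives the number of wounds, saying that the robotic and video-assisted "techniques both use three to four incisions".

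Section 2.1 lists the weight rule among the steps taken to limit risk: "dosing of Standard Bupivacaine will be based upon subject weight", with a reference to Section 8.3.2. The documents do not explain why 35 kg was chosen, and they give no other cut-off and no separate mg/kg limit for heavier subjects.

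**The concern.** A per-kilogram maximum for light subjects should begin to bind at the weight where the fixed dose reaches it. Here it begins 2.5 kg too low. The prepared dose steps up at the cut-off, and the highest mg/kg dose in the scheme goes to subjects just above 35 kg, who are light themselves. A subject of 35 to under 37.5 kg can therefore receive more Standard Bupivacaine per kilogram than the maximum set for anyone lighter.

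What is at stake is a dosing safeguard, not an inference. Section 2.1 attributes most serious adverse events to dose-related causes, inappropriate dosing among them. It relies on weight-based dosing together with the hepatic exclusion, aspiration before injection, telemetry and mental-status checks. The documents do not call 2 mg/kg a toxicity limit, so the point is confined to the mismatch between the cut-off and the stated maximum.

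**Working it through.** **Inputs**

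- Concentration 2.5 mg/cc, total volume 60 cc (Sections 8.3.1 and 8.3.2).
- Fixed volume at 35 kg or more: 30 cc (Sections 8.3.1 and 8.3.2, Table 1).
- Maximum below 35 kg: 2 mg/kg (same places).
- Injection: 5 cc into each of spaces 3 to 10, which is eight spaces, and into each wound (Section 8.4.1, read as 5 cc per wound).
- Wounds: three or four (Section 6.2).

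**The plan's own figure**

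30 cc × 2.5 mg/cc = 75 mg. This reproduces Table 1.

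**Where 75 mg meets 2 mg/kg**

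75 mg ÷ 2 mg/kg = 37.5 kg.

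**Prepared dose around the cut-off**

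| Weight (kg) | Dose under the rule (mg) | mg/kg | 2 mg/kg would be (mg) | Excess |
|---|---|---|---|---|
| 34.9 | at most 69.8 (27.9 cc) | at most 2.00 | 69.8 | none |
| 35 | 75 | 2.14 | 70 | 5 mg (7.1%) |
| 36 | 75 | 2.08 | 72 | 3 mg (4.2%) |
| 37 | 75 | 2.03 | 74 | 1 mg (1.4%) |
| 37.5 | 75 | 2.00 | 75 | none |

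**Delivered dose at 35 kg or more**

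The prepared solution holds 75 mg ÷ 60 cc = 1.25 mg/cc, and the eight spaces take 8 × 5 = 40 cc.

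- Four wounds: 40 + 20 = 60 cc, so 60 × 1.25 = 75 mg. At 35 kg this is 75/35 = 2.14 mg/kg, and 2 mg/kg is reached at 75/2 = 37.5 kg.
- Three wounds: 40 + 15 = 55 cc, so 55 × 1.25 = 68.75 mg. At 35 kg this is 68.75/35 = 1.96 mg/kg, and 2 mg/kg is reached at 68.75/2 = 34.4 kg.

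The 35 kg cut-off thus keeps the delivered dose within 2 mg/kg for three wounds but not for four. The step at the cut-off is present even with three wounds: a 34.9 kg subject prepared at the maximum receives 69.8 × 55/60 = 63.98 mg, or 1.83 mg/kg, against 1.96 mg/kg at 35 kg.

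Reading Section 8.4.1 as 5 cc per wound fits the preparation: eight spaces plus four wounds is 12 sites, and 12 × 5 = 60 cc.

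**The case against.** The best reply is that no written rule is broken. The 2 mg/kg maximum is stated only for subjects under 35 kg, each weight has exactly one instruction, and a 36 kg subject given 75 mg is dosed as the protocol directs. Nor do the documents claim that 35 kg was calculated as 75/2. On that view this is an unexplained threshold, not a miscalculation. All of this is true as far as it goes. But a maximum that the next instruction exceeds, with no reason given, does not do the work of a maximum, and all three statements of the rule share the fault.

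The reach is also small. With three wounds the delivered dose stays below 2 mg/kg. The affected band is 2.5 kg wide in a trial of 80 adults, and the investigator may exclude anyone whose safety would be compromised (Section 6.3, criterion 10). In the test arm the prepared bupivacaine products total 266 + 75 = 341 mg, the 266 mg is not weight-adjusted, and 5 mg is about 1.5% of that total (5/341). These points stand. They limit the importance of the mismatch without removing it.

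**Conclusion.** The cut-off and the maximum are misaligned. The prepared dose exceeds 2 mg/kg from 35 kg to just under 37.5 kg, by at most 5 mg (7.1%). The delivered dose exceeds it by the same amount with four wounds and not at all with three. The delivered figures assume 5 cc per wound; the prepared-dose figures need no assumption.

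The point is minor. The documents give no weight distribution, so it is not shown that any subject in the band would enrol, and no safety consequence is demonstrated. The rule is identical in both arms, so the comparison, power and alpha are untouched.

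**What to change.** Replace 35 kg by 37.5 kg in Section 8.3.1, Section 8.3.2 and the Table 1 footnote. Subjects of 37.5 kg or more then get 30 cc, and lighter subjects get no more than 2 mg/kg. An equivalent wording is 2 mg/kg up to 75 mg, at every weight. Either removes the step.

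Keeping 35 kg and lowering the fixed dose to 70 mg (28 cc) would also align the rule, but it would change the dose for almost every subject and is not recommended.

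The cost is one number in three places. The saline volume already varies to make up 60 cc. A 36 kg subject, for example, would get up to 72 mg (28.8 cc) with 60 − 28.8 = 31.2 cc saline in the control arm, or 60 − 20 − 28.8 = 11.2 cc in the test arm. Sample size, blinding and analysis do not change.

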8.3.3 Packaging and Labeling

Study drugs (Liposomal Bupivacaine and Standard Bupivacaine) will be labeled with the required FDA warning statement, the protocol number, the subject number, and directions for use. As Standard Bupivacaine is clear and Liposomal Bupivacaine is milky white, obscuring over-wraps will be placed over syringe. The inpatient pharmacy will prepare and deliver the drug to the operating room.

8.4 Supply of Study Drug at the Site

Study drugs (Liposomal Bupivacaine and Standard Bupivacaine) are already stocked and available at the inpatient pharmacy for use in the operating room.

8.4.1 Dosage/Dosage Regimen

See Sections 8.3.1 and 8.3.2 for Drug Preparation.

Liposomal Bupivacaine

- 5cc of drug preparation will be injected into each intercostal space 3-10 and subcutaneously into each wound.

Standard Bupivacaine

- 5cc of drug preparation will be injected into each intercostal space 3-10 and subcutaneously into each wound.

8.4.2 Dispensing

The inpatient investigational pharmacist will dispense the drugs to the operating room.

8.4.3 Administration Instructions

Liposomal Bupivacaine

- 5cc of prepared drug will be percutaneously injected into each intercostal space 3-10 with a 22-gauge spinal needle under direct intrathoracic vision and subcutaneously into each wound at the conclusion of the surgery.

Standard Bupivacaine

- 5cc of prepared drug will be percutaneously injected into each intercostal space 3-10 with a 22-gauge spinal needle under direct intrathoracic vision and subcutaneously into each wound at the conclusion of the surgery.

Prior to injection, the investigator will aspirate to ensure that the tip of the needle is not in the intravascular space.

8.4.4 Storage

Study drugs will be stored per inpatient pharmacy standards.

8.5 Study Drug Accountability

An accurate and current accounting of the dispensing and return of study drug for each subject will be maintained on an ongoing basis by a member of the study site staff. The number of study drug dispensed and returned by the subject will be recorded on the Investigational Drug Accountability Record. The study monitor will verify these documents throughout the course of the study.

8.6 Measures of Treatment Compliance

Subject compliance is not an issue with this study as the treatment is given in a single episode by the investigators at the conclusion of surgery. A standardized approach will be

used by all investigators as outlined in Section 8.4.3. To ensure that each subject receives the same postoperative pain management, a standardized electronic orderset will be utilized.

9 STUDY PROCEDURES AND GUIDELINES

A Schedule of Events representing the required testing procedures to be performed for the duration of the study is diagrammed in Appendix 1.

Prior to conducting any study-related activities, written informed consent and the Health Insurance Portability and Accountability Act (HIPAA) authorization must be signed and dated by the subject.

9.1 Clinical Assessments

9.1.1 Concomitant Medications

All concomitant medication will be documented at the preoperative and postoperative clinic visits. Dose, route, unit frequency of administration, and indication for administration and dates of medication will be captured.

9.1.2 Demographics

Demographic information (date of birth, gender, race) will be recorded at the preoperative clinic visit.

9.1.3 Medical History

Relevant medical history, including history of current disease and information regarding underlying diseases will be recorded at the preoperative clinic visit.

9.1.4 Physical Examination

A complete physical examination will be performed by either the investigator or a subinvestigator who is a physician within the Department of Surgery, Division of Cardiothoracic Surgery. Qualified staff (MD, NP, RN, and PA) may complete the abbreviated physical exam at all other visits. New abnormal physical exam findings must be documented and will be followed by a physician or other qualified staff at the next scheduled visit.

9.1.5 Vital Signs

Body temperature, blood pressure, pulse and respirations will be performed after resting for 5 minutes at the preoperative and postoperative clinic visits.

9.1.6 Other Clinical Procedures

Subjects will be given the Short Form-8-Health Survey at the preoperative and postoperative clinic visits. In addition, subjects will be given a Pain Medication Survey at the postoperative clinic visit to capture what medications are still being used to control pain.

9.1.7 Adverse Events

Information regarding occurrence of adverse events will be captured throughout the study. Duration (start and stop dates), severity, outcome, treatment, and relation to study drug will be recorded on the case report form (CRF).

9.2 Clinical Laboratory Measurements

9.2.1 Pregnancy Test

A urine pregnancy test will be obtained from female subjects who are of childbearing age on the day of their surgery.

10 EVALUATIONS BY VISIT

10.1 Visit 1 – Preoperative Clinic Visit

1. Review the study with the subject and obtain written informed consent and HIPAA authorization.
2. Assign the subject a unique screening number.
3. Record demographics data.
4. Record medical history, including indication for surgery and prior thoracic surgeries.
5. Record concomitant medications.
6. Perform a complete physical examination.
7. Perform and record vital signs.
8. Obtain routine preoperative studies as clinically indicated, including pulmonary function tests, cardiology evaluation, chest imaging (CT, PET-CT, MRI), bronchoscopy with endoscopic ultrasound, and lung biopsy.
9. Administer Short Form-8-Health Survey
10. Schedule subject for surgery.

10.2 Visit 2 – Surgery with Hospitalization

1. Collect urine pregnancy test in female patients of childbearing age in the preoperative suite.
2. Randomize to Liposomal Bupivacaine or Standard Bupivacaine during surgery.
3. Administer intervention during surgery.
4. Record any Adverse Experiences and/or Review subject diary for adverse experiences and exclusionary medication use daily.
5. Concomitant medications administration.
6. Perform abbreviated physical examination daily.
7. Perform and record vital signs every 4 hours.
8. Monitor with Continuous Pulse Oximetry and Continuous Cardiac Monitoring throughout hospitalization.

10.3 Visit 3 – Postoperative Clinic Visit

1. Record any Adverse Experiences.
2. Record changes to concomitant medications.
3. Perform abbreviated physical examination.
4. Perform and record vital signs.
5. Administer Short Form-8-Health Survey and Pain Medication Survey.

11 ADVERSE EXPERIENCE REPORTING AND DOCUMENTATION

11.1 Adverse Events

An adverse event (AE) is any untoward medical occurrence in a clinical investigation of a patient administered a pharmaceutical product and that does not necessarily have a causal relationship with the treatment. An AE is therefore any unfavorable and unintended sign (including an abnormal laboratory finding), symptom or disease temporally associated with the administration of an investigational product, whether or not related to that investigational product. An unexpected AE is one of a type not identified in nature, severity, or frequency in the current Investigator's Brochure or of greater severity or frequency than expected based on the information in the Investigator's Brochure.

The Investigator will probe, via discussion with the subject, for the occurrence of AEs during each subject visit and record the information in the site's source documents.

Adverse events will be recorded in the patient CRF. Adverse events will be described by duration (start and stop dates and times), severity, outcome, treatment and relation to study drug, or if unrelated, the cause.

AE Severity

The National Cancer Institute's Common Terminology Criteria for Adverse Events (CTCAE) Version 3.0 will be used to assess and grade AE severity, including laboratory abnormalities judged to be clinically significant. The modified criteria can be found in the study manual. If the experience is not covered in the modified criteria, the guidelines shown in Table 1 below should be used to grade severity. It should be pointed out that the term "severe" is a measure of intensity and that a severe AE is not necessarily serious.

Table 1. AE Severity Grading

| Severity (Toxicity Grade) | Description |
|----------------------------------|---|
| Mild (1) | Transient or mild discomfort; no limitation in activity; no medical intervention or therapy required. The subject may be aware of the sign or symptom but tolerates it reasonably well. |
| Moderate (2) | Mild to moderate limitation in activity, no or minimal medical intervention/therapy required. |
| Severe (3) | Marked limitation in activity, medical intervention/therapy required, hospitalizations possible. |
| Life-threatening (4) | The subject is at risk of death due to the adverse experience as it occurred. This does not refer to an experience that hypothetically might have caused death if it were more severe. |

AE Relationship to Study Drug

The relationship of an AE to the study drug should be assessed using the following the guidelines in Table 2.

Table 2. AE Relationship to Study Drug

| Relationship to Drug | Comment |
|-----------------------------|---|
| Definitely | Previously known toxicity of agent; or an event that follows a reasonable temporal sequence from administration of the drug; that follows a known or expected response pattern to the suspected drug; that is confirmed by stopping or reducing the dosage of the drug; and that is not explained by any other reasonable hypothesis. |
| Probably | An event that follows a reasonable temporal sequence from administration of the drug; that follows a known or expected response pattern to the suspected drug; that is confirmed by stopping or reducing the dosage of the drug; and that is unlikely to be explained by the known characteristics of the subject's clinical state or by other interventions. |
| Possibly | An event that follows a reasonable temporal sequence from administration of the drug; that follows a known or expected response pattern to that suspected drug; but that could readily have been produced by a number of other factors. |
| Unrelated | An event that can be determined with certainty to have no relationship to the study drug. |

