12 DISCONTINUATION AND REPLACEMENT OF SUBJECTS

12.1 Early Discontinuation of Study Drug

Early discontinuation of study drug is not applicable as study drug is given in a single episode.

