15.4 Analysis of Secondary Endpoints

- Cumulative Daily In-Hospital Pain Score (0-10)
- Mean Time to First Opioid Use (hours)
- Mean Time to Ambulation (hours)
- Pulmonary Complications: Pneumonia and Atelectasis requiring Bronchoscopy (y/n)
- Liposomal Bupivacaine and Stand Bupivacaine Adverse Events (y/n):
 - Gastrointestinal- nausea, emesis, constipation
 - Hypersensitivity- pruritis, urticaria, anaphylaxis
 - Cardiac- atrioventricular heart block, cardiac arrest
 - Neurologic- dizziness, altered mental status, seizure
 - Miscellaneous

Safety and tolerability data will be summarized by treatment group. Adverse event rates will be coded by body system and will include the number of patients for whom the event occurred, the rate of occurrence, and the severity and relationship to study drug.

- Length of Stay (days)
- Total Opioid Prescription at Discharge (morphine equivalents in mg)
- Total Opioid Use as Outpatient (morphine equivalents in mg)
- Direct Costs of hospital encounter (dollars)
- Quality of life – Short-Form-8 Health Survey (Optum Health)

Student's t-test, Pearson's chi-squared test, and Kaplan-Meier survival estimate will be used. A 2-sided alpha error set at 0.05 will be used to assess for statistical significance.

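### The relatedness grades in section 11.1, Table 2 do not fit a single-dose drug: Probably cannot be met, and Definitely is either too easily met or also out of reach

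*Combined protocol and SAP*

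**What the plan says.** Section 11.1 tells assessors to grade each adverse event's relationship to study drug using the guidelines in Table 2, which has four levels.

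- *Definitely* opens with two alternatives: "Previously known toxicity of agent; or an event that follows a reasonable temporal sequence from administration of the drug". A list of further conditions follows, including "that is confirmed by stopping or reducing the dosage of the drug".
- *Probably* requires timing, a known or expected response pattern, and then an event "that is confirmed by stopping or reducing the dosage of the drug; and that is unlikely to be explained by the known characteristics". The row goes on to name the patient's own condition and concurrent treatment as the competing explanations.
- *Possibly* requires timing and a known or expected pattern, "but that could readily have been produced by a number of other factors". It has no dose-stopping condition.
- *Unrelated* is "An event that can be determined with certainty to have no relationship to the study drug".

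On dosing, section 12.1 states: "Early discontinuation of study drug is not applicable as study drug is given in a single episode". Section 8.6 agrees: "the treatment is given in a single episode by the investigators at the conclusion of" surgery.

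Relatedness is recorded for every event on the CRF (sections 9.1.7 and 11.1). Section 15.4 lists it among the safety results, which are to include "the severity and relationship to study drug". Section 14.1 has it tabulated for the DMC.

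**The concern.** The table appears to be written for a drug given repeatedly, where an assessor can withdraw or lower the dose and watch the event. Here nothing is left to withdraw once the block and wound infiltration are done. One of the four grades is therefore closed by its own definition, and the grade above it depends on how a single *or* is read.

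This matters because the listed toxicities of both drugs overlap with opioid effects. Sections 2.1 and 14.1 name nausea, emesis and constipation as the commonest events. Section 7.1 makes as-needed oxycodone and hydromorphone available to every subject in hospital, and oxycodone at discharge. Section 2 says over 15% of inpatients on oxycodone have altered mental status, nausea or constipation. The purpose of a relatedness grade is to separate these causes, and as written the table cannot do so consistently.

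**Working it through.** No sample-size, power or error-rate figure bears on this point, and the plan gives no figure to reproduce. The check sets each row of Table 2 against the single-dose statements in sections 8.6 and 12.1.

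**Step 1. Can each grade be met?**

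| Grade | Key conditions | With one dose |
|---|---|---|
| Definitely, known toxicity taken alone | Known toxicity only | Met by any listed toxicity |
| Definitely, remaining route | Timing, pattern, dose stopped or reduced, no other reasonable explanation | Cannot be met |
| Probably | Timing, pattern, dose stopped or reduced, other explanation unlikely | Cannot be met |
| Possibly | Timing, pattern, other factors could readily explain it | Can be met |
| Unrelated | Certainty of no relationship | Can be met only with certainty |

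The conditions for *Probably* are joint, so failing one fails the grade.

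**Step 2. The two readings of *Definitely*.**

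- *Literal reading.* The *or* makes known toxicity sufficient, without the listed conditions on response pattern, dose stopping or other causes.
- *Whole-row reading.* The later conditions also apply to known toxicities. The dose-stopping condition is then required throughout, and *Definitely* is unattainable, like *Probably*.

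Either one upper grade is over-inclusive and the other empty, or both are empty.

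**Step 3. How many subjects could the literal reading touch?**

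Inputs: more than 10% of subjects expected to have nausea, emesis or constipation (sections 2.1 and 14.1), and 80 subjects (section 15.6).

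0.10 × 80 = 8, so more than 8 subjects are expected to have such an event. This counts subjects whose events *could* be graded *Definitely*. It does not predict how they will be graded, because the same event in a subject taking opioids also fits *Possibly*, and the table gives no rule for choosing.

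**Step 4. Does every event have a grade?**

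*Possibly* needs a known or expected response pattern, and *Unrelated* needs certainty. An event that fits no known pattern but cannot be ruled out with certainty meets neither. It also fails *Probably* and both routes to *Definitely*, so it has no grade.

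**Step 5. Where does the grade feed in?**

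It feeds the relatedness entry of the section 15.4 safety summary and the DMC tabulation in section 14.1. It does not feed the following:

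- the primary endpoint (section 5.1);
- the yes/no adverse-event endpoint (section 5.2);
- SAE documentation and reporting, which are regardless of causality (sections 11.2.1 and 17.2);
- real-time reporting, which is triggered by event type (section 11.3);
- the stopping provisions (sections 14.1 and 15.5), which do not mention relatedness.

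**The case against.** The strongest reply is that Table 2 is offered as guidelines, so an experienced assessor will pass over a condition that plainly cannot apply. An assessor may also treat an event that fades as the drug clears as meeting it. The first half of this stands: judgement may soften the effect, and it is too strong to say the reported grades must be wrong. The second half does not, because the wording asks for an act of stopping or reducing the dose. Leaving each assessor to decide which conditions to ignore is itself what makes the column unreliable.

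A second reply is that the literal reading of *Definitely* is uncharitable, and that section 11.1 already ties an adverse event to temporal association with dosing. That is fair, and it is why the row is called ambiguous here. The alternative reading does not rescue the table, since it closes *Definitely* altogether.

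A reader might also infer several stronger things that the documents do not support:

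- *That no milder grade is available.* *Possibly* remains open and suits nausea or constipation in a subject on opioids.
- *That everything left over falls into* Possibly. That grade has its own timing and pattern conditions, so some events fall into no grade.
- *That a predictable number of subjects will be graded* Definitely. Only the number with a qualifying event can be bounded. The 15% figure in section 2 is an oxycodone rate that includes altered mental status, so it cannot serve as a rate for the block.
- *That the DMC's safety signal or the trial's safety conclusion is distorted.* The DMC also sees events compared between arms, with intensity, seriousness and individual events of concern.
- *That one arm is favoured.* Both preparations contain bupivacaine (sections 8.3.1 and 8.3.2), section 2.1 calls the risks similar, and section 8.2 blinds investigators. Nothing in the documents shows differential misgrading.

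**Conclusion.** The point holds as an error in the text as written, and it is minor. *Probably* cannot be assigned to any event under its own definition. *Definitely* is either met by known toxicity alone or cannot be met, depending on how its *or* is read. Some events have no grade. On the literal reading, the ambiguity reaches the commonest listed toxicities, expected in more than 8 of 80 subjects.

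The consequence is an unreliable relatedness column in the section 15.4 summary and the DMC tables. Efficacy results, event counts by arm and expedited reporting are untouched, and no between-arm bias is shown.

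The conclusion assumes that assessors apply Table 2 broadly as written, and that no document outside the protocol adapts it to a single dose. The protocol itself contains no such adaptation.

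**What to change.** In section 11.1, Table 2:

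1. Delete the condition about stopping or reducing the dose from both *Definitely* and *Probably*.
2. Replace the stand-alone known-toxicity alternative in *Definitely* with one joint rule: a known toxicity, with reasonable timing, and with no other reasonable explanation.
3. Optionally, reword *Unrelated* so that it does not demand certainty, or add a level between it and *Possibly*, so that every event has a grade. The number of levels is a matter of preference; the aim is only that none is left without a home.
4. Align the relationship field on the CRF with the revised table.

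The cost is an edit to one table and a matching check of the CRF, handled as a protocol amendment under section 17.1. It needs no new data or visits and does not change treatment. Any events already graded would need their relatedness reassessed, while still blinded, under the revised wording.
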